Review/record AEs ^y			X																		
Prior and concomitant medications		X																			

Abbreviations: ADA=antidrug antibodies; AE=adverse event; BMI=body mass index; D=day; ECG=electrocardiogram; Echo=echocardiography; eGFR=estimated glomerular filtration rate; EOT=end of treatment; FSH=follicle-stimulating hormone; ICF=informed consent form; LFT=liver function test; PD=pharmacodynamics; PK=pharmacokinetic; Q=every; SC=subcutaneous.

Notes:

- When scheduled at the same time points, the assessments of vital signs and 12-lead ECGs must be performed first, before the physical examinations, blood sample collections, and urine collections.
- Assessments should be performed predose, where applicable, unless otherwise noted.

- Grey columns indicate the study day when the 24-hour urine collection for PD analysis should begin. Patients may be admitted to the clinical study center to complete the 24-hour urine collections.
 - a. Patients will be invited to participate in an open-label extension study once they complete the postdose follow-up period on Study Day 141. For patients who do not enroll in the open-label extension study, safety and PD follow-up will continue until plasma glycolate is <20% above baseline or \leq the ULN AND 24-hour urinary oxalate is >80% of baseline, or until the SRC makes a decision per investigator request to discontinue follow-up on a case-by-case basis. The decision cannot be made until after completion of the postdose follow-up period (84 days after last dose).
 - b. Patients initially randomized to placebo may continue in the study receiving administration of open-label ALN-GO1 according to the Schedule of Assessments (Table 3). Patients will be unblinded on or after Day 78.
 - c. Complete medical history (including documentation or confirmation of PH1) will be obtained at screening and any changes will be updated on Day -1. AEs occurring after signing of the ICF and before study drug administration will be captured as medical history.
 - d. See Section 7.5.3 for assessments to be performed during a full physical examination or symptom-directed physical examination.
 - e. During screening and at EOT, height will be measured for all patients; thereafter, height will only be measured for patients <18 years of age. Additionally, for patients <18 years of age, at each time point, height will be measured in centimeters, and in triplicate, to facilitate calculation of eGFR using the Schwartz Bedside Formula.

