Important potential risks to healthy subjects and patients include injection site reactions (ISRs). Other potential risks include: embryofetal toxicity, coagulation abnormalities, and liver function test abnormalities. These potential risks have been reduced by the specific inclusion and exclusion criteria incorporated into the selection of healthy subjects as well as for patients with PH1 in this clinical study.

No data are available on the use of ALN-GO1 in pregnancy; however, human mutagenicity is not suggested based on the available nonclinical data (see Investigator's Brochure for further information). Embryofetal risk is limited by requiring that women of childbearing potential (WOCBP) must have a negative pregnancy test, cannot be breast feeding, and must be willing to use a highly effective method of contraception as specified in the protocol. Male subjects/patients are not required to use the contraception measures required for female study subjects/patients. No male contraception is considered to be required.

The occurrence of ISRs will be carefully monitored.

Nonclinical studies in rats showed mild to moderate decreases in fibrinogen and occasionally minimal prolonged prothrombin time without accompanying clinical or microscopic evidence of hemorrhage. This effect is likely species-specific as it was not observed in NHPs and will be monitored via clinical laboratory safety assessments.

As ALN-GO1 is a hepatically-targeted therapeutic, liver function tests will be carefully monitored. Nonclinical data suggest that there is a wide margin between the proposed clinical doses and any hepatic findings in toxicology studies and that any findings can be monitored. The potential non-specific, off-target risk of ALN-GO1 administration is considered to be low, based on nonclinical toxicological assessment of this molecule and accumulating experience with this RNA interference (RNAi) therapeutics platform.

During the course of this study, safety will be monitored by study Investigators, the Sponsor Medical Monitor, and a SRC. The initial dose level for administration in the MAD part of the study will have been previously shown to be safe, tolerable, and pharmacologically active based on SRC review of safety and PD data from the SAD part of the study. Stopping rules have also been designed to protect study participants.

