8.2.5. Pharmacodynamic Analyses

For Part A, PD analysis will be the comparison of change from baseline in plasma glycolate concentration for each subject in ALN-GO1 dose groups and placebo.

For Part B, PD analysis will be the comparison of the change from baseline in urinary oxalate excretion (oxalate concentration in 24-hour urine collection), with additional analyses of the change from baseline in urinary glycolate excretion (glycolate concentration in 24-hour urine collection), plasma glycolate concentration, and calculated creatinine clearance, for each patient in active dose groups and placebo.

The PD parameters will be summarized using descriptive statistics for actual results and relative to baseline for each follow-up time points.

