7.2.3 By-visit Data Presentation

In Part B, the by-visit PD and safety summaries will be presented according to the specifications below.

Monthly Dosing Regimen: Part B

Timepoint ^a	Placebo ^b	Monthly	Monthly	Monthly	Monthly	Monthly	Monthly
	(N=4)	ALN-GO1	ALN-GO1	ALN-GO1	ALN-GO1	ALN-GO1	ALN-GO1
		Single-blind ^c	Comb.d	Single-blind ^c	Comb.d	Single-blind ^c	Comb.d
		Dose1	Dose1	Dose2	Dose2	Total	Total
		(N=3)	(N=4 or 8)	(N=3)	(N=4 or 8)	(N=6)	(N=8 or 16)
Baselinee							
Day 29							
Day 57							
Day 85 ^f							
Day 113	NA						
Day 141	NA						
Day 169 ^g	NA						
Day 197 ^h	NA						
Day 225	NA						
Day 253	NA						
Day 281	NA						
Day 309	NA						

- a: In monthly dosing regimen, patients randomized to ALN-GO1 will be summarized by study day 1 to 85 during the single-blind monthly treatment period, then by post dosing follow-up period after Day 85 and up to Day 169, followed by Safety and PD follow-up after Day 169. Patients randomized to Placebo will be summarized by study day 1 to 85 relative to placebo dosing date during the single-blind treatment period. Data collected after the first dose of ALN-GO1 will be summarized separately by days relative to the first open-label ALN-GO1 dose with all visits for the rest of the study mirrored to the patients randomized to the single-blind ALN-GO1. These data will be summarized in combination with data from patients randomized to ALN-GO1 at each corresponding visit.
- b: Patients from all monthly and quarterly dosing cohorts randomized to placebo at study start
- c: Patients randomized to ALN-GO1 at study start receiving ALN-GO1 in single-blind manner
- d: Patients receiving ALN-GO1 in single-blind or open-label manner and in any sequence combined
- e: Baseline is defined as before first dose date/time of each treatment, placebo or ALN-GO1
- f: Day 85 is the end of treatment period
- g: Day 169 is the end of post-treatment follow-up period
- h: Day 197 and later visits are Safety and PD follow-up visits

Quarterly Dosing Regimen: Part B

Timepointa	Placebob	Quarterly	Quarterly	Quarterly	Quarterly	Quarterly	Quarterly	Quarterly	Quarterly	Quarterly
	(N=4)	2-doses ^c	1-dose ^d	Comb.e	2-doses ^c	1-dose ^d	Comb.e	2-doses ^c	1-dose ^d	Comb.e
		ALN-GO1	ALN-GO1	ALN-GO1	ALN-GO1	ALN-GO1	ALN-GO1	ALN-GO1	ALN-GO1	ALN-GO1
		Dose1	Dose1	Dose1	Dose2	Dose2	Dose2	Total	Total	Total
		(N=3)	(N=1)	(N=4)	(N=3)	(N=1)	(N=4)	(N=6)	(N=2)	(N=8)
Baselinef										
Day 29										
Day 57										
Day 85g										

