7.4.3 Clinical Laboratory Assessments

Where applicable, abnormal laboratory results will be graded according to NCI CTCAE v4.0. A shift table, presenting the 2-way frequency tabulation for baseline and the worst post-baseline value according to the NCI CTCAE grade, will be provided for selected clinical laboratory tests. Both scheduled and unscheduled post-baseline values will be considered.

For Part A, descriptive statistics will be provided for clinical laboratory data for actual results, changes from baseline, and relative to the upper limit of normal range (ULN) over time by pooled placebo and ascending ALN-GO1 dose.

For Part B, descriptive statistics will be provided for clinical laboratory data for actual results, changes from baseline and relative to the upper limit of normal range over time according to the data display specification in Section 7.2.

Clinical laboratory tests with normal ranges will be classified as Low, Normal, and High. For these tests, abnormal values will be flagged in the listings with H when the value is higher than the upper limit of the reference ranges and with L when the value is lower than the lower limit of the reference ranges.

This categorical data will also be summarized in shift tables comparing the worst value post-baseline with those at the baseline visit. When there are both high and low abnormal values for a subject for a particular laboratory variable, the worst value will be taken (the value furthest outside of the normal ranges, or the first value experienced, if this value is the same). In Part A, frequencies and percentages will be presented by dose group. In Part B, shift table will be

summarized by pooled placebo and ascending single-blind ALN-GO1 dose and by ALN-GO1 dose in single-blind and open-label combined.

All clinical laboratory data in Part A and Part B will be listed.

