7.6 Pharmacodynamic and Exploratory Analyses

Pharmacodynamic parameters will be measured from blood and urine samples collected at times outlined in the Schedule of Assessments in both Part A and Part B. PD analyses will be based on the Pharmacodynamic Analysis Sets.

24-hour urine oxalate content corrected for BSA will be calculated as:

[24-hour urine oxalate in mmol/L]*[24-hour urine volume recorded in CRF in ml] /(1000 ml per L)*24hours/[actual collection time calculated from CRF in hours] *1.73/[patient BSA]

Where patient BSA will be calculated as:

Patient BSA = sqrt([mean height in cm] *[weight in kg]/3600).

24-hour urine creatinine clearance corrected for BSA will be calculated as:

[24-hour urine creatinine concentration in mg/dl]*[24-hour urine volume recorded in CRF in ml]

/[Plasma creatinine in mg/dl]/[actual collection time calculated from CRF in minutes] *1.73/[patient BSA]24-hour urine oxalate/creatinine ratio will be calculated as:

24-hour urine oxalate concentration (mg/L) /24-hour urine creatinine concentration (mg/dL)/10.

For Part A and Part B, the mean and standard error of actual values and changes from baseline in plasma and urine glycolate will be plotted over time by ALN-GO1 dose level and placebo. In

addition, plots will be provided for plasma and urine glycolate of individual subjects by dose level of ALN-GO1 and placebo.

For Part B, the mean and standard error of actual values and changes from baseline in urinary oxalate per 24-hour urine collection and urinary creatinine per 24-hour urine collection will be plotted over time. In addition, the plots will be presented separately by ADA status. Plasma glycolate concentration and oxalate/creatinine ratio will be plotted in the same manner. For patients randomized to placebo, figures will include PD measurements up to the first dose of open-label study drug.

For other PD variables in Part A and B, descriptive statistics will be provided for actual results, change from baseline, and percent change from baseline. For Part B, the PD summaries will be presented according to the data display specification in Section 7.2.3.For Part A and Part B, Cmax and AUCt of plasma glycolate will be presented with descriptive statistics and percent coefficient of variation [%CV]) by regimen and ascending dose level and placebo presented first.

In Part A and Part B, all PD data will be listed by regimen, dose, ADA status (Part B only) and subject/patient.

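### The SAP's Part B by-visit tables have no rows for labs on Days 2, 15 and 43 or plasma PD on Days 15 and 43, and the SAP ends the monthly postdose period at Day 169 where the protocol ends it at Day 141

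*SAP*

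**What the plan says.** **By-visit rows.** SAP 7.2.3 sets the layout for Part B: "In Part B, the by-visit PD and safety summaries will be presented according to the specifications below". Both of its tables, monthly and quarterly, list baseline and Days 29, 57, 85, 113, 141, 169 and so on to Day 309. SAP 7.4.3 gives Part B lab data as actual results, "changes from baseline and relative to the upper limit of normal range over time according to the data display specification in Section 7.2"; within 7.2, only 7.2.3 lists visits. SAP 7.6 is explicit for PD: "For Part B, the PD summaries will be presented according to the data display specification in Section 7.2.3".

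Protocol 8.2.5 says the PD parameters will be "summarized using descriptive statistics for actual results and relative to baseline for each follow-up time points". Protocol 8.2.7 asks for lab values and changes from baseline over time. SAP Section 9 declares no change from the protocol's analysis.

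**Period boundary.** For monthly cohorts, SAP 7.2.2 runs postdose follow-up from after Day 85 to Day 169. Footnote a to the monthly table in 7.2.3 repeats this. Footnote g reads "g: Day 169 is the end of post-treatment follow-up period", and footnote h starts the Safety and PD follow-up visits at Day 197. Protocol Table 2, footnote a, invites patients to the extension study "once they complete the postdose follow-up period on Study Day 141". Footnotes i and l of the same table call Day 169 the first visit or first day of Safety and PD Follow-up.

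**The concern.** In monthly cohorts the visits without a row are the lab and plasma PD visits that fall inside a dosing interval. The by-visit means, changes from baseline and multiples of ULN would then describe only the end of each interval. Protocol 1.5 names coagulation and liver function test abnormalities as potential risks and says: "As ALN-GO1 is a hepatically-targeted therapeutic, liver function tests will be carefully monitored". A rise in liver enzymes that peaks and settles within four weeks of a dose would not show in any by-visit lab mean or change against pooled placebo.

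The boundary matters because the SAP also summarises safety data by period. SAP 7.4.1 refers its AE summaries to the periods in 7.2.1 and 7.2.2. SAP 7.4.6 reports ECGs separately for postdose follow-up and for Safety and PD follow-up. SAP 7.4.4 refers vital signs to the same definitions. A boundary 28 days too late puts data into the wrong period.

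**Working it through.** No sample-size or power figure is involved. The check compares scheduled days with table rows.

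**Inputs.** Lab, plasma PD and 24-hour urine rows of protocol Tables 2 (monthly) and 4 (quarterly); visit rows of SAP 7.2.3; monthly dosing on Days 1, 29 and 57, and quarterly dosing on Days 1 and 85 (SAP 7.4.2); the note to Tables 2 and 4 that assessments are predose where applicable.

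**Step 1: visits after Day 1 with and without a row.**

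| Measure and window | Scheduled days | Days without a row | Share |
|---|---|---|---|
| Monthly labs, to Day 85 | 2, 15, 29, 43, 57, 85 | 2, 15, 43 | 3/6 = 50% |
| Monthly plasma PD, to Day 85 | 15, 29, 43, 57, 85 | 15, 43 | 2/5 = 40% |
| Monthly 24-hour urine, to Day 85 | collections starting 28, 56, 84 (visits 29, 57, 85) | none | 0/3 |
| Quarterly labs, to Day 141 | 2, 15, 29, 43, 57, 85, 86, 99, 113, 127, 141 | 2, 15, 43, 86, 99, 127 | 6/11 = 55% |
| Quarterly plasma PD, to Day 141 | 15, 29, 43, 57, 85, 99, 113, 127, 141 | 15, 43, 99, 127 | 4/9 = 44% |

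Plasma PD is not scheduled on Day 2 or Day 86, so those two days concern labs only.

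**Step 2: time since the preceding dose, monthly.** Rows present: 29 − 1 = 28, 57 − 29 = 28 and 85 − 57 = 28 days. Days 29 and 57 are predose, so all three rows are end-of-interval. Rows absent: 2 − 1 = 1, 15 − 1 = 14 and 43 − 29 = 14 days.

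**Step 3: the same for quarterly.** Days 29, 57 and 85 are 28, 56 and 84 days after the Day 1 dose, so the rows present already sample the interval. The end-of-interval point therefore applies to monthly cohorts only.

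**Step 4: crossover patients.** With open-label ALN-GO1 starting on Day 85, relative day = study day − 85 + 1. Study Days 86, 99 and 127 become relative Days 2, 15 and 43, so the same rows serve these patients.

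**Step 5: period boundary.** The last monthly dose is on Day 57, and the minimum postdose follow-up is 84 days: 57 + 84 = 141, as in Table 2. For crossover patients, Table 3 ends the period at study Day 225, and 225 − 84 = 141 relative to the first ALN-GO1 dose; its first Safety and PD Follow-up visit, Day 253, is relative Day 169. The SAP's 169 equals 85 + 84, that is, 84 days counted from the end of its dosing analysis period, not from the last dose. Of the 169 − 85 = 84 days in the SAP's postdose period, 169 − 141 = 28 (one third) belong to the next period under the protocol.

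**The case against.** The strongest reply is that little is lost.

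- **Other outputs carry the values.** SAP 7.4.3 builds lab shift tables on the worst post-baseline value; the CTCAE version counts scheduled and unscheduled results. All labs are listed. SAP 7.6 plans mean and individual glycolate plots over time, plasma glycolate Cmax and AUCt, and full PD listings, none of them limited to the 7.2.3 rows. This stands. A reader might infer that the data are dropped, that an early glycolate rise is lost, or that a liver signal would go unseen; the documents support none of these. What is missing is the by-visit statistic: a shift table gives a category without its timing, and a listing gives no summary against placebo.
- **The first-named PD analysis is untouched.** The listed rows match the 24-hour urine schedule, so urinary oxalate loses no scheduled visit. This stands, but the SAP does not say that the table is meant for urine measures only.
- **The protocol conflict covers PD only.** For labs, protocol 8.2.7 says only over time. This stands; the lab part is a gap in presentation. Yet SAP 7.4.6 summarises ECG parameters at every scheduled time, and labs have no such wording.
- **The tables are partly shells, and cells are small.** Single-blind cells have 3 patients per dose, one footnote still holds a placeholder, and SAP 8.2 leaves table format to a separate document. This softens the point, but a section that sets the specification should list the right visits.
- **The SAP follows Amendment 4, not the current protocol.** This does not rescue Day 169: the Amendment 4 change log shows that Table 2 already called it the first Safety and PD Follow-up visit. The reply does bar a stronger reading, that Day 169 contains only patients who did not enter the extension. That rests on the Amendment 5 rollover rule; under Amendment 4, rollover also needed urinary oxalate or 12-month criteria. Nor are by-visit statistics mixed, since Days 113, 141 and 169 have separate rows.

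**Conclusion.** The point holds in two limited parts.

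First, the by-visit specification leaves out scheduled lab and plasma PD visits: 3 of 6 and 2 of 5 in monthly cohorts through Day 85, and 6 of 11 and 4 of 9 in quarterly cohorts through Day 141. In monthly cohorts, every on-treatment by-visit lab and plasma PD summary is at 28 days postdose. For plasma PD this departs from protocol 8.2.5 without being declared.

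Second, the SAP's monthly postdose period ends 28 days after the protocol's, which affects period-based AE, vital-sign and ECG summaries. The effect is clearest for ECGs, where the two follow-up periods are reported separately; SAP 7.4.4 can be read as pooling them for vital signs, in which case that table would not change.

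This rests on reading the 7.2.3 rows as the full visit list and on the column positions in protocol Tables 2 and 4. It is worth correcting before the tables are programmed, but it does not affect data collection or the 24-hour urine results.

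**What to change.** 1. In SAP 7.2.3, add rows by parameter. Labs: Days 2, 15 and 43, plus Days 86, 99 and 127 for quarterly cohorts. Plasma PD: Days 15 and 43, plus Days 99 and 127 for quarterly cohorts. Leave the 24-hour urine rows as they are, so that no empty rows appear.
2. Align crossover patients by day relative to first ALN-GO1 dose. Quarterly rows 86, 99 and 127 then apply only to patients randomised to ALN-GO1.
3. In SAP 7.2.2, and in footnotes a, g and h of the monthly table in 7.2.3, end monthly postdose follow-up at Day 141 and make Day 169 the first Safety and PD Follow-up visit, both relative to first ALN-GO1 dose.

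The cost is a few extra table rows and one corrected period boundary. No new data are needed.

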7.3 Study Population Data

7.3.1 Subject and Patient Disposition

For Part A, the following subject disposition categories will be summarized, if applicable:

- Subjects who were randomized,
- Subjects who were randomized but not treated,
- Subjects who were randomized and treated,
- Subjects who completed/did not complete the single-blind treatment, and
- Subjects who completed/did not complete the study.

Patient disposition will be summarized by initial ALN-GO1 dose level and regimen and in total for all subjects in Part B. Patients in randomized cohorts

For Part B, the following patient disposition categories will be summarized, if applicable:

- Patients who were enrolled,
- Patients who were enrolled but not treated,
- Patients who were enrolled and treated,
- Patients who completed/did not complete the initial/all treatment,
- Patients who completed/did not complete the study.

Patients that signed the informed consent form and met applicable eligibility criteria will be considered as enrolled. For those who did not complete study treatment per protocol and/or did not complete the study, the primary reason for withdrawal will be summarized.

The number and percentage of subjects in each defined analysis population will be tabulated and presented.

All subject disposition data will be presented in a data listing for both Part A and Part B.

7.3.2 Protocol Deviations

All major protocol deviations will be presented in a data listing.

7.3.3 Demographic and Baseline Characteristics

In Part A and Part B, demographic and baseline characteristics will be summarized by regimen (as applicable in Part B) and ascending dose level groups, placebo, and in total for the Safety Analysis Sets. If the PK and PD Analysis Sets contain a different set of subjects/patients compared to those included in the Safety Analysis Set, then demographic information will be summarized separately for those analysis sets.

The following variables will be considered based on their collection at screening. Gender, race, and ethnicity will be summarized with contingency tables. Age at screening (years), height, weight, and body mass index (BMI) at baseline will be presented with appropriate summary statistics (n, mean, median, SD, minimum, maximum). See Section 6.1.3 for height and weight baseline definition. Patients <18 years of age at screening Part B will have the modified z-score calculated for their height, weight, and BMI according to the Centers for Disease Control growth chart [1] and will be presented with summary statistics.

For Part B patients, the 24-hour urinary oxalate excretion (mmol/24 hours/1.73m²) and eGFR at baseline will be summarized descriptively by dose level groups, placebo, and in total. Separate analyses will be provided for patients less than 18 years of age and patients 18 years or older at informed consent.

The number and percentage of subject who took vitamin B6 within 90 days of informed consent and/or during the study will be tabulated.

Summary tables will be presented by ascending ALN-GO1 dose level with subjects/patients receiving placebo pooled across enrollment cohort and in total.

By-subject data listings of demographic information will be presented for Part A and Part B.

